7.9.3 Laboratory values

Laboratory variables are not collected as part of the regular study visits. However, baseline values from the REFALS end-of-study visit will be summarised with descriptive statistics. See [REFALS SAP](#) for further definitions.

7.9.4 12-lead ECG

Descriptive statistics of standard 12-lead ECG variables and abnormal ECG findings will be tabulated by treatment group for each study visit.

Disjoint comparisons of heart rate changes from baseline to the thresholds of > 20 bpm and > 30 bpm will be summarised by treatment group at each study visit.

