1.3.2 Potential risks associated with levosimendan

Safety data with oral levosimendan are primarily based on treatment of patients with heart failure and extensive experience with the i.v. preparation, although 66 patients with ALS received levosimendan in the LEVALS study. Available data indicate that levosimendan or its active metabolites do not typically cause clinically significant direct CNS effects. Headache (due to vasodilatation), increased heart rate and palpitations have been the most commonly reported adverse drug reactions in healthy subjects and/or ALS patients treated with levosimendan. Myocardial and arterial changes such as hypertrophy, myocarditis and vasculitis have been observed in toxicity studies in animal species, dog being the most sensitive species with first signs of toxicity appearing at 2-5 fold clinical exposure. The clinical relevance of these findings is not known. Based on the safety data originating from the completed clinical studies with oral levosimendan in chronic heart failure (CHF) (administered 1-2 mg daily for longer than 180 days), safety signals of increased heart rate and palpitations have been detected and are considered as potential risks for oral levosimendan use. No other safety concerns related to cardiac function have been identified from these data. Arrhythmias are known AEs for i.v. levosimendan in patients with severe CHF. However, there is no such evidence for oral levosimendan in healthy subjects. In addition, in the LEVALS, phase IIa study conducted in ALS patients, no differences in supraventricular or ventricular tachyarrhythmias were seen between placebo and levosimendan treatments. There were no differences either in the numbers of severe AEs or serious adverse events (SAEs) between the treatments. However, special attention should be paid to symptoms potentially connected with cardiac arrhythmias, such as palpitations, dizziness and loss of consciousness. In laboratory parameters, slight decreases in red cell parameters and serum potassium have been observed in some studies.

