6.4.5 Laboratory safety assessments

A pregnancy test for female subjects of childbearing potential will be performed at baseline and at each study centre visit during the treatment period and at the end-of-study visit.

Local safety laboratory tests may be performed if clinically indicated (for example in assessment of an AE).

Instructions for the collection, handling, storage and transportation of samples will be provided before the start of the study.

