8.4.5.3 Laboratory safety analysis

In case recorded, laboratory values and changes from baseline will be summarised using descriptive statistics.

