6. GENERAL STATISTICAL CONSIDERATIONS

6.1 Data sets to be analysed

All analyses will be performed in the safety population, including subjects who receive at least 1 dose of study treatment. No other analysis populations are planned.

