7.1 Disposition of subjects

329 subjects completed the REFALS study. Of those, 28 were ineligible to continue to the extension study, and 54 otherwise eligible subjects did not wish to continue. Of the remaining 247 subjects who wished to continue, 20 were delayed due to COVID-19 related restrictions, and did not start the study before the recruitment was closed. In total, 227 subjects were screened and started the extension.

The number of subjects will be tabulated by treatment group for the following populations:

- Screened population
- Safety population
- Discontinued study

Separate tables by treatment group will also be provided for each country, and each study centre.

The disposition and number of subjects, along with reasons for screening failure and study discontinuations, will be listed and tabulated by treatment group.

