7.9.2 Adverse events

Adverse events (AEs) will be classified by system organ classes (SOC) and preferred terms (PTs) using the MedDRA dictionary version 23.1.

A treatment-emergent AE (TEAE) is defined as any event arising or worsening after the start of study drug administration until 25 days after the last study medication intake.

A summary of TEAEs and non-TEAEs will be presented, showing total numbers of events and subjects having events:

1. Fatal outcome
2. SAE status
3. Other significant AEs
4. AESI status
5. Causality
6. Severity
7. Actions taken

The number of TEAEs, and number and proportion (%) of subjects having TEAEs by SOC and PT will be given by treatment group. The number of events will also be broken down by:

1. Severity (mild, moderate, severe)
2. Causality (related, not related)
3. Timing with respect to starting treatment (disjoint union of: ≤ 2 weeks, ≤ 4 weeks, ≤ 8 weeks, ≤ 12 weeks, ≤ 24 weeks, ≤ 48 weeks)
4. Dose change groups (see 7.4)

Incidence rates for subjects' first events adjusted for exposure time will also be reported. They are calculated by dividing the number of subjects ever experiencing the event while on treatment by the number of days subjects were exposed to the study treatment.

All serious adverse events (SAEs) and other significant AEs will be evaluated case by case. Narrative descriptions will be included in the study report for all AEs leading to death, other SAEs, AEs leading to study treatment withdrawal, and certain other significant AEs (OSAEs).

Groups of treatment emergent AEs of special interest (AESIs) are defined by Standardized MedDRA Queries (SMQs) where noted, and by in-house search categories (IHSCs) defined as lists of preferred terms, otherwise. Statistics for the following AESIs will be reported:

1. Asthenia or fatigue
2. Decrease in red cell parameters
3. Drug related hepatic disorders - comprehensive search (SMQ)
4. Haemorrhages (SMQ)
5. Headache
6. Hypokalaemia (SMQ)
7. Hypotension
8. Increased heart rate
9. Ischaemic heart disease (SMQ)
10. Neurocognitive disorder
11. Palpitations
12. Suicide/self-injury (SMQ)
13. Supraventricular tachyarrhythmias (SMQ)
14. Ventricular tachyarrhythmias (SMQ)

See Appendix 10.2 for the queries used to create the groups. If an SMQ has both a broad and a narrow definition, the narrow search will be used.

In addition to standard AE reporting, detailed characteristics will be reported for AESIs:

1. SAE status
2. Need for concomitant medications
3. Severity

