4. Changes in dosage
5. Outcome
6. Timing with respect to starting treatment
7. Duration of event
8. Safety subgroups (listed in 6.2.14)

Further, for AESIs, 95% confidence intervals (CIs) will be reported for incidence proportions and incidence rates, and risk ratios and incidence rate ratios (with 95% CIs) between the treatment groups will be estimated.

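### AESIs detected mainly by blood tests get incidences, 95% CIs and between-arm ratios over all dosed subjects, although no haematology or chemistry is scheduled after the first dose

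*SAP*

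**What the plan says.** **Known signal.** Protocol 1.3.2: "In laboratory parameters, slight decreases in red cell parameters and serum potassium have been observed in some studies".

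**AESIs.** The list in SAP 7.9.2 includes "Decrease in red cell parameters", hypokalaemia (an SMQ) and drug-related hepatic disorders (the comprehensive-search SMQ). The search definitions are in Appendix 10.2, which holds only a link.

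**Reporting.** SAP 7.9.2: "for AESIs, 95% confidence intervals (CIs) will be reported for incidence proportions and incidence rates". Risk ratios and incidence rate ratios between treatment groups, with 95% CIs, are added. The groups are the former REFALS arms (SAP 7).

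**Denominators.** SAP 6.1: "All analyses will be performed in the safety population, including subjects who receive at least 1 dose of study treatment". The exposure-adjusted rate divides subjects with the event by days of exposure. Neither denominator depends on having been tested.

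**Laboratory schedule.** SAP 7.9.3: "Laboratory variables are not collected as part of the regular study visits". Protocol Table 1 places haematology and chemistry at the REFALS end-of-study visit only, and Table 2 (treatment period) has no row for them. The COVID-19 table in Protocol 6.5 adds them at Visit 1 if they were missed or entry was delayed. It has none at the telephone visit that replaces a 3-monthly visit. On treatment, Protocol 6.4.5 says: "Local safety laboratory tests may be performed if clinically indicated (for example in assessment of an AE".

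**Laboratory summary.** For any values that are recorded, Protocol 8.4.5.3 says that "laboratory values and changes from baseline will be summarised using descriptive statistics". SAP 7.9.3 keeps only the baseline values from the REFALS end-of-study visit.

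**The concern.** A mild fall in haemoglobin or potassium usually causes no symptom that would prompt a test. Without a schedule, such an event enters the AE data only if someone had another reason to draw blood. Subjects never tested stay in the denominator and contribute exposure days without an event.

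Long-term safety is the primary objective, and the protocol itself names two of these effects. A low count with a tight interval could be read as reassurance on a question the extension was not set up to answer. The same applies to the combined AE summary in SAP 7.10.4. REFALS had laboratory tests at regular intervals over 48 weeks (Protocol 1.1), so a lower frequency in the extension could simply reflect the end of scheduled testing.

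**Working it through.** **1. Denominator.** The counts in SAP 7.1 reproduce: 329 − 28 − 54 = 247 wished to continue, and 247 − 20 = 227. The SAP states: "In total, 227 subjects were screened and started the extension".

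**2. Can a scheduled sample reveal an event?** A TEAE must arise or worsen after the first dose (SAP 7.9.2). The only scheduled haematology and chemistry come before that dose. By itself, therefore, no scheduled sample can reveal a treatment-emergent laboratory event; detection depends on for-cause testing.

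**3. Direction of the error in the incidence.** Let p be the true proportion with the effect and s the share of those cases that are detected. The expected reported proportion is s × p, which is below p unless every case is found. The rate has the same problem, because its numerator shrinks while all exposure days remain. If testing were random with a share f tested, s would equal f. With for-cause testing s may exceed f. Neither s nor f is in the documents.

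**4. Scale with no events.** The exact (Clopper-Pearson) two-sided 95% upper limit for 0/n is 1 − 0.025^(1/n). For n = 227 it is 1.61%. That limit is valid for the frequency of *reported* events. It bounds the frequency of the *effect* only if nearly all cases would have been detected.

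**5. Illustration with events (assumptions: p = 10%, f = 25%, random testing).** Tested: 0.25 × 227 ≈ 57. Events found: 0.10 × 57 ≈ 6. The SAP calculation gives 6/227 = 2.6%, exact 95% CI 1.0% to 5.7%, which excludes the assumed 10%. Other tested shares at p = 10%:

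| Share tested (assumed) | Events found | Proportion over 227 |
|---|---|---|
| 100% | 23 | 10.1% |
| 50% | 11 | 4.8% |
| 25% | 6 | 2.6% |
| 10% | 2 | 0.9% |

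**6. Ratios.** If the detected shares in the two former arms are s1 and s0, the expected risk ratio is (p1 × s1)/(p0 × s0). With s1 = s0 it is unbiased. Take an assumed 151:76 split (227 at the 2:1 REFALS allocation), p = 10% in both arms, and SE of log RR = √(1/a − 1/n1 + 1/b − 1/n0), where a and b are the expected events:

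- All cases detected: a = 15.1, b = 7.6, RR 1.0, 95% CI 0.44 to 2.29.
- 25% detected in both arms: a = 3.78, b = 1.9, RR 1.0, 95% CI 0.18 to 5.59.
- 25% against 50%: RR = 0.25/0.50 = 0.5. Reversed: 2.0.

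Bias in the ratio thus needs unequal detection. Equal under-detection costs only precision.

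**7. Protocol against SAP.** Protocol 8.4.5.3 covers recorded values and their changes from baseline; SAP 7.9.3 covers baseline alone. SAP 7.11 says in general terms that reporting was narrowed to descriptive statistics. The dropped item is itself descriptive, so that statement does not explain its removal. Conversely, the AESI intervals and ratios survive, although SAP 6.2.2 marks significance level and confidence intervals as not applicable. SAP section 9 says the plan was drafted from the REFALS SAP, so a carry-over is a likely explanation, but this is an inference.

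**The case against.** AESIs here are reported adverse events grouped by search terms, not laboratory thresholds. For the proportion of treated subjects with a *reported* event, all treated subjects is the ordinary denominator, and under-detection affects any spontaneously reported AE to some degree. Lighter monitoring is deliberate (Protocol 1.2.1), SAP 7.9.3 discloses it, no hypothesis is tested, and REFALS supplies scheduled laboratory data. All of this stands, and it is why the counts should be kept. It does not justify an interval and a ratio that look like estimates of an effect's frequency when the means of detecting it was withdrawn and no caveat is planned.

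Four stronger readings are tempting, and the documents do not support them:

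- *All three AESIs need blood tests.* The hepatic term list is not in the documents and may include clinical diagnoses. The claim is strongest for red cell parameters and hypokalaemia.
- *The risk ratio merely compares testing habits.* All subjects receive levosimendan under the same visit rules, and the documents give no reason to expect testing to differ between former arms.
- *The 1.6% bound is too tight by a definite factor.* Any factor needs an assumed tested share and random testing. Protocol 6.4.5 makes testing for cause.
- *The denominator should be the subjects tested.* They are tested because a problem is suspected, so their proportion would probably overstate incidence.

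It is also not stated that normal local results enter the eCRF, so the number tested may not be fully recoverable.

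**Conclusion.** The point holds for decrease in red cell parameters and hypokalaemia, and probably for part of the hepatic group. Read as the frequency of the effect, the planned incidences are biased downward and their intervals are too narrow around too low a value. The ratios lose precision and are biased only under unequal testing.

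The amount of bias cannot be computed, because the documents do not give the share tested. The one firm figure is the 1.6% upper limit for 0/227; the results in steps 5 and 6 are illustrations. The conclusion rests on two things: that these events are found mainly through laboratory results, and that the SAP applies its general denominators to them, as its text implies. The omission of recorded on-treatment values is a separate, smaller departure from the protocol that SAP 7.11 does not name.

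**What to change.** - **SAP 7.9.2.** For the laboratory-detected AESIs (red cell parameters, hypokalaemia, and the hepatic terms that are laboratory findings), report counts of reported events only. Omit the CIs, risk ratios and rate ratios. Label the events as clinically detected and not systematically ascertained.
- **SAP 7.10.4.** Carry the same label into the combined AE summary, noting that REFALS had regular laboratory tests and the extension did not.
- **SAP 7.9.3.** Restore the Protocol 8.4.5.3 summary, or a listing, of any recorded on-treatment values and their change from the REFALS end-of-study value. Give the number of subjects with such a value by former arm, where recorded. Do not turn it into a tested-only incidence.
- **SAP 7.11.** If the summary is not restored, name its removal and give the reason.

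The cost is SAP wording and one extra table or listing, which may be sparse. No new procedure is needed. The safety statements for these AESIs will look less favourable.

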6.4 Safety assessments

6.4.1 Adverse events

6.4.1.1 Definitions

An AE is any untoward medical occurrence in a study subject administered a pharmaceutical product and which does not necessarily have a causal relationship with this treatment. An AE can therefore be any unfavourable and unintended sign (including an abnormal laboratory finding), symptom, or disease temporally associated with the use of an investigational medicinal product, whether or not related to the investigational medicinal product. The definition also covers medication errors and uses outside what is foreseen in the protocol, including misuse and abuse of the product.

Thus, an AE may be an appearance or worsening of any undesirable sign or symptom, any worsening of the current medical conditions or onset of a new disease, compared with the previous observations or a clinically significant adverse change in a laboratory variable or other diagnostic finding (e.g. ECG).

In this study, symptoms that the investigator considers to be due to expected progression of ALS are not considered as an AE, except for disease progression leading to death during the study.

An SAE is any untoward medical occurrences that at any dose

- results in death
- is life-threatening
- requires inpatient hospitalisation or prolongation of existing hospitalisation (see section 6.4.1.3 for exclusions)
- results in persistent or significant disability/incapacity
- is a congenital anomaly/birth defect, or
- is an important medical event jeopardizing the patient or requiring intervention to prevent serious outcome (examples of such events are intensive treatment in an emergency room or at home for allergic bronchospasm; blood dyscrasias or convulsions that do not result in hospitalisation; development of drug dependency or drug abuse; overdose or interaction).

Other significant AEs are marked haematological and other laboratory abnormalities (other than those meeting the definition of serious) and any events that lead to an intervention, including

- withdrawal of the investigational product
- reduction of its dose
- significant additional concomitant therapy

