6.2.8 Multiple measurements

Here, a multiple measurement refers to a combination of analysis visit and timepoint where there are more than one value recorded for a given parameter.

If there are multiple measurements for a given parameter-visit-timepoint combination, values from the measurement that was performed last will be used.

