6.2.9 Multiple timepoints

Visits following the Week 2 (and possible Week 4) site visit(s) and the Week 6 TC will be binned based on time elapsed since the baseline visit; visits falling into the same interval of time will be given the same label for reporting. The binning will be done on a monthly level, with visit days rounded to the nearest full month, using a conversion factor of 1 month = 30.4375 days.

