7.10.4 Combined analyses with the main study

Additional analyses combining the data collected in REFALS with the data collected in REFALS-ES will be performed outside the scope of the clinical study report. This section outlines the currently planned analyses.

The primary population used for combined reporting will be the REFALS safety population.

REFALS study baseline characteristics will be reported for the REFALS-ES safety population.

Descriptive statistics for change from REFALS baseline will be reported for supine SVC, ALSFR-R and Borg endpoints, as well as vital signs (pulse rate, systolic and diastolic blood pressure).

Descriptive statistics for supine SVC and ALSFRS-R endpoints over the course of both studies will be reported in relevant efficacy subgroups identified in the REFALS study.

Random slope models will be fitted using data from both studies to estimate the rate of decline in supine SVC and ALSFRS-R endpoints over an extended follow-up period. A time-by-study-by-arm interaction will be investigated to potentially identify a change in slopes for the placebo arm transitioning over to active treatment for REFALS-ES.

Kaplan-Meier curves will be estimated for the time-to-event endpoints described in 7.5.2.2, and additionally time to invasive ventilation (tracheostomy or intubation) or death, and time to death. Estimation will start from the REFALS baseline and continue until the end of the extension study.

Adverse events and the number of deaths over the course of both studies will be summarised.

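### SAP 7.9.4 counts abnormal ECG findings visit by visit only, so for findings not reported as AEs the number of subjects newly or ever abnormal generally cannot be read from the planned tables

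*SAP*

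**What the plan says.** SAP 7.9.4 plans two ECG outputs. The first covers ECG variables and abnormal findings: "Descriptive statistics of standard 12-lead ECG variables and abnormal ECG findings will be tabulated by treatment group for each study visit". The second is "Disjoint comparisons of heart rate changes from baseline" to thresholds of more than 20 and more than 30 bpm, again at each visit.

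The material for a within-subject comparison exists. Protocol Table 1 has an ECG at the REFALS end-of-study visit, SAP 6.2.7 takes pre-dose values from the baseline visit as baseline, and Protocol 6.4.4 requires an ECG at each centre visit during treatment.

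Two general rules decide which ECGs enter the table. SAP 6.2.9: "Visits following the Week 2 (and possible Week 4) site visit(s) and the Week 6 TC will be binned based on time elapsed", by rounding to the nearest month of 30.4375 days. SAP 6.2.8: "If there are multiple measurements for a given parameter-visit-timepoint combination, values from the measurement that was performed last will be used".

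The combined analyses in SAP 7.10.4 cover supine SVC, ALSFRS-R, Borg scores, time-to-event endpoints, AEs and deaths, "as well as vital signs (pulse rate, systolic and diastolic blood pressure"). They name no ECG findings. Protocol 8.4.5.2 says only that abnormal ECG findings will be summarised.

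**The concern.** Long-term safety is the primary objective. Protocol 1.3.2 lists increased heart rate and palpitations as potential risks, notes arrhythmias with the intravenous form in severe heart failure, and asks for attention to symptoms that may point to arrhythmia. For repeated ECGs the natural safety questions are how many subjects developed an abnormality they did not have on entry, and how many had one at any time on treatment. Counts per visit are prevalences. They do not link a subject's ECG to that subject's baseline or to the same subject's other visits.

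The SAP uses the linked forms elsewhere. Suicidality is summarised by visit and over the whole study (7.10.2), blood pressure and pulse categories join a threshold to a change (7.9.5), and treatment-emergent AEs are those arising or worsening after treatment start (7.9.2). Abnormal ECG findings get neither a change from baseline nor an any-time count.

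**Working it through.** The plan gives no figure to reproduce. The check is what by-visit counts can identify, and which ECGs reach the table.

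**1. New cases at one visit.** Take n subjects with an ECG at baseline and at a given visit. Let a have the finding at baseline and b at the visit. The number with the finding at the visit but not at baseline is at least max(0, b − a) and at most min(b, n − a), and both limits can be reached.
- If a = b, new cases can be anything from 0 (the same people) to min(a, n − a) (as little overlap as possible). A stable count does not show that no one became abnormal.
- If a = 0, both limits equal b and the table does answer the question for that visit. The other cases in which the limits meet are trivial: nobody has the finding at the visit, or everybody has it at one of the two times.
- Outside a = 0 the table is weaker still, because its baseline column includes subjects not seen at the later visit.

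**2. Any time on treatment.** Suppose the same n subjects are seen at k visits, with counts b₁ to bₖ. The number ever abnormal lies between the largest bⱼ and min(n, b₁ + … + bₖ). The number ever newly abnormal lies between max(0, largest bⱼ − a) and min(n − a, b₁ + … + bₖ). With more than one visit, even a = 0 does not generally fix the any-time count. Flexible visits and dropout put different subjects in different columns, which adds uncertainty.

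**3. Which ECGs are tabulated.** I take the monthly label of SAP 6.2.9 as the analysis visit to which SAP 6.2.8 applies. The label is day / 30.4375, rounded.
- Centre visits on days 91 and 105: 91 / 30.4375 = 2.99 and 105 / 30.4375 = 3.45. Both are month 3, and the day 91 ECG is dropped.
- Centre visits on days 91 and 108: 108 / 30.4375 = 3.55, which is month 4. Both ECGs are kept.

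So an abnormal ECG can be replaced by a later normal one, for instance at a reassessment after a dose change. These days only show that it can happen. Protocol 6.1.3 allows the reassessment by telephone and does not say how often it is done at a centre, so no frequency follows.

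**4. Other routes to a subject-level count.** The AE definition in Protocol 6.4.1.1 includes "a clinically significant adverse change in a laboratory variable or other diagnostic finding (e.g. ECG"). Such a change enters the SAP 7.9.2 tables as a number and percentage of subjects. It may also fall in an AE group of special interest: increased heart rate, palpitations, ischaemic heart disease, or supraventricular or ventricular tachyarrhythmias. A finding judged below that line enters none of these. No shift, new-since-baseline or any-time ECG count appears elsewhere in SAP 7.9 or in 7.10.4.

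**The case against.** The strongest reply is that the clinically important part is already covered, and this stands. Significant ECG changes are AEs. Events leading to "reduction of its dose" are other significant AEs, and "All serious adverse events (SAEs) and other significant AEs will be evaluated case by case". The special-interest groups receive incidence proportions and rates with 95% confidence intervals and between-arm ratios. Protocol 4.3 excludes new or significantly worsened serious cardiovascular disease at entry. What remains is findings the investigator did not report.

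A reader might infer that the SAP falls short of the protocol. It does not: Protocol 8.4.5.2 asks for a summary without naming a form, and SAP 7.11 openly narrows reporting after the main study's results and early termination.

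A reader might also infer that ECGs around the planned dose increase are lost. The documents do not support this. The week 2 and possible week 4 site visits lie outside the monthly bins, and an ordinary telephone contact includes no ECG (Protocol Table 2), so it replaces none.

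Finally, the subject-level counts could be derived later, and SAP 7.13 mentions subject data listings. That is true, but no ECG listing or derivation is specified. The reply lowers the weight of the point without removing it.

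**Conclusion.** The point holds as a modest weakness of method. For ECG findings not reported as AEs, the planned tables generally cannot give the number of subjects newly abnormal since extension baseline or abnormal at any time on treatment. The last-value rule within monthly bins can hide some findings as well.

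No size can be stated. SAP 7.1 gives 227 subjects starting the extension, but neither document gives an ECG abnormality rate, the share of abnormal ECGs reported as AEs, or the share of reassessments done at a centre. The limits above include zero new cases whenever the visit count does not exceed the baseline count. It would go too far to conclude that a cardiac signal will be missed: the AE route is intact, and nothing shows that unreported findings are common or important.

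The conclusion rests on two readings: that for each study visit in SAP 7.9.4 means per-visit counts only, and that the monthly label is the analysis visit in SAP 6.2.8. Priority is low; the case for acting is that the remedy is cheap and serves the primary objective.

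**What to change.** Keep the by-visit table. Add one descriptive table to SAP 7.9.4, by REFALS arm and in total, using all on-treatment ECGs before the last-value rule is applied. It should show:
- the shift from extension baseline (normal, abnormal) to the worst on-treatment ECG;
- the number and percentage of subjects with a new abnormality, among those normal at baseline with at least one on-treatment ECG;
- exposure time or the number of on-treatment ECGs alongside.

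Break the counts down by type only if findings are recorded in categories. Protocol section 7 does not list ECG findings among the coded data, so this needs checking first.

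Add a footnote that new means new since the off-treatment extension baseline. Prior-levosimendan subjects reach that baseline after a 14–25 day break, so a finding that cleared in the break and returned would count as new without being new since first exposure.

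The cost is one table from data already collected, within the descriptive scope of SAP 7.11, and no planned output is removed. The table has limits: a worst-value count rises with the number of ECGs, ECGs are analysed locally (Protocol 9.4), so reading may differ between centres, and there is no concurrent control. It should be read as description, not as evidence of a drug effect.
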